6.5 SUB-GROUP ANALYSES

If there are enough study participants in specific racial/ethnic categories and or urban/rural and/or age group categories, the study team will perform the planned analyses for the primary efficacy analyses within subgroups.

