3.3 SAMPLE SIZE

The primary outcome for this study is the proportion of unvaccinated children who complete the COVID-19 vaccine series during the study period. The underlying assumption, based on available data for ISPCTN site states, is that without the mHealth intervention, the COVID-19 vaccine uptake would occur in 30% of children.¹

Justification of primary outcome effect size. Table 1 summarizes vaccination rates among children 12-17 years old through July 31, 2021, as published by the CDC.² Based on these data, we see that vaccination rates decline with decreasing age and that ECHO ISPCTN states demonstrate a trend toward lower overall and by-age vaccination rates. When excluding Vermont, Rhode Island, and New Hampshire (states that are part of the highest regional vaccine uptake rates in the US), the other 15 ECHO ISPCTN states have vaccination rates significantly lower than non-IDeA states. Assuming that cumulative vaccination rates continue to increase over time and that vaccination rates for children <12 years old will continue the trend toward lower vaccination rates, we anticipate that 30% overall vaccination rates among eligible children at the time of study launch is reasonable.

Table 1. Proportion of Children 12-17 yrs. old who completed COVID-19 vaccination by July 31, 2021				
	12-17 Med[IQR]	16-17 years old	14-15 years old	12-13 years old
Overall	30% [25%-42%]	40% [32%-51%]	29% [24%-41%]	24% [19%-34%]
IDeA State Residents	24% [20%-37%]	33% [26%-49%]	23% [19%-35%]	20% [14%-32%]
IDeA State Residents (excluding New England)	23% [19%-36%]*	31% [26%-45%]	22% [18%-29%]	19% [14%-31%]
Non-IDeA State Residents	32% [25%-42%]	41% [32%-51%]	29% [24%-41%]	25% [19%-34%]

*Difference from non-IDeA state residents (p=0.028)

We based the 10% increase in vaccination rates on the cumulative estimated effects of intervention components within the Vaccine Uptake app. As discussed in the Background, behavioral nudges such as text messages (i.e., push notifications within the app) are associated with a 5% increase in vaccination rates.³ App-based education and communication has shown variable increases in vaccination rates and intent to vaccinate, up to 8-10%.^{4,5} Thus, a combined 10% increase in vaccination rates is reasonable to expect from the Vaccine Uptake app since it combines multiple approaches in the same intervention.

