Public Health Impact. In this study, we are estimating that using the Vaccine Uptake app will result in a 10% increase in the proportion of children who will complete COVID-19 vaccination. When looking at the impact of a 10% increase in pediatric vaccination rates, based on a US population of 53.7 million children 5-17 years of age,⁶ such an increase would result in an additional 5 million vaccinated children. Previous research has shown that app-based vaccine uptake interventions are less costly than more traditional methods, such as paper handouts and communication tools. We estimate a cost of \$10,000 dollars for the first year of a customized version of the

Vaccine Uptake app per state. Deployment of the Vaccine Uptake app nationally would cost a little as \$500,000 dollars per year, or 10 cents per additional child who completes COVID-19 vaccination.

In determining sample size, each caregiver is considered to be a cluster with an average of 2 unvaccinated children. To demonstrate an improvement in the proportion of unvaccinated children of caregivers who complete the COVID-19 vaccination series due to the mHealth intervention from 30% to 40%^{7,8,9} would require 758 caregivers (379 per arm), at the two-sided 0.05 significance level with power of 0.90 and an intraclass correlation coefficient of 0.60. The table below shows the sample size needed to have 90% power to detect a 10-percentage point increase in the proportion of children who complete the vaccination series using the Vaccine Uptake app with varying levels of intraclass correlation. To ensure that there are at least 758 caregivers, the primary analysis population, we expect to randomize 892 caregivers to account for up to 15% of randomized participants who do not use the Vaccine Uptake app or General Health app after downloading it during enrollment.

Intraclass Correlation Coefficient	Sample Size
0.40	331 per arm (662 total)
0.50	355 per arm (710 total)
0.60	379 per arm (758 total)
0.70	402 per arm (804 total)
0.80	426 per arm (852 total)

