5.2 STATISTICAL SIGNIFICANCE AND CONFIDENCE INTERVALS

Unless otherwise specified, statistical tests will be 2-sided for all analyses and the null hypothesis will be rejected at the significance level of $\alpha = 0.05$. P-values will be rounded to four decimal places before assessing statistical significance. All confidence intervals presented will be 95% and two-sided.

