6.2 ANALYSIS OF THE PRIMARY EFFICACY ENDPOINT

For the primary efficacy measure, we will test the following null hypothesis:

H₀: Vaccination series completion rate among children of caregivers assigned to the Vaccine Uptake app will not differ from the vaccine series completion rate among children of caregivers assigned to the General Health app

vs

H₁: Unvaccinated children of caregivers assigned to the Vaccine Uptake app will be more likely to achieve COVID-19 vaccine series completion than those children whose caregivers are assigned to the General Health app

For each vaccine-eligible child, the primary endpoint will be whether or not the child initiates and completes the COVID-19 vaccine series during the 24 weeks of the intervention period. The study team will define vaccine series completion as per the current ACIP guidance for the vaccine product. For children who receive a product that requires more than 2 doses for the primary series, receipt of up to 3 doses will be considered complete. Vaccine doses will only be valid for study purposes if given within the 24 weeks of study participation. Additional doses, when required for primary series completion, will only be valid if they are in accordance with ACIP-recommended interval minus a 4-day grace period, in accordance with recommendations of the ACIP. Also, per ACIP, there will be no maximum interval between valid doses. Incorrect second vaccine product (i.e., mixed series) will be invalid for study purposes.

Univariate Analysis

The primary endpoint will be collected as a dichotomous variable (yes/no). We will report the probability of COVID-19 vaccine series completion for each intervention group (Vaccine Uptake app vs General Health app). Initially, an unadjusted non-modeling approach using SAS PROC FREQ will be used estimate the relative risk (RR) for COVID-19 vaccine series completion (with Wald 95% CI), with the General Health app intervention group as the reference group. The analysis will be performed for all three populations (ITT, mITT, and PP).

Primary and Multivariable Analysis

A mixed-effect Poisson regression with robust error variance will be used to report adjusted relative risk (RR) with 95% CI accounting for site random effect and controlling for clustering by caregiver. The multivariable model will allow adjustment for covariates. The analysis will be performed for all three populations (ITT, mITT, and PP).

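### Subgroups are to be examined only by repeating the primary analysis within each one; with no test of whether the app effect differs, chance differences can readily be read as effect modification

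*SAP*

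**What the plan says.** SAP 6.5 sets a condition, "If there are enough study participants in specific racial/ethnic categories and or urban/rural and/or age group categories", and then one method: the team will "perform the planned analyses for the primary efficacy analyses within subgroups". Protocol 11.4.7 carries the same plan. Neither section defines subgroup levels, age cut-points or a minimum size.

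The analysis to be repeated is in SAP 6.2: "A mixed-effect Poisson regression with robust error variance will be used to report adjusted relative risk (RR) with 95% CI", with a site random effect and allowance for clustering by caregiver. On other terms, SAP 6.2 says only: "The multivariable model will allow adjustment for covariates". No arm-by-subgroup term is named. An unadjusted RR precedes the model, and both analyses are run in the ITT, mITT and PP populations.

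SAP 5.2 applies to subgroups as to everything else: "statistical tests will be 2-sided for all analyses and the null hypothesis will be rejected at the significance level of" 0.05. No interaction or heterogeneity test for subgroups appears in either document. Protocol 11.4.10 relates demographic factors, including rurality, to vaccination by logistic regression. That asks who gets vaccinated, not for whom the app works better.

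**The concern.** Whether an effect differs between two groups is a question about the difference between two estimates. Running the same test in each group answers two other questions, each with less power than the trial has overall. When the true effect is the same everywhere, one group will often cross the 0.05 line and the other will not, simply because each is smaller than the whole trial.

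Readers will look hard at these subgroups. The rationale (Protocol 2.1 and 2.2) centres on rural and underserved communities, recruitment gives priority to rural and minority families (Protocol 7.1 and 7.1.1), and the app content is tailored by rurality, race/ethnicity and child's age (Protocol 1.1). Those are the same three factors as in SAP 6.5. A result that seems to show the app working in one community and not in another could steer its deployment, and the plan offers no valid check on it.

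**Working it through.** **Inputs from SAP 3.3, SAP 3.2.1 and Protocol 11.2.** Control rate 30% ("without the mHealth intervention, the COVID-19 vaccine uptake would occur in 30% of children"), app rate 40%, ICC 0.60, an average of 2 children per caregiver, two-sided alpha 0.05, power 0.90, 1:1 allocation, 758 caregivers needed and 892 randomized. Subgroup shares are not given, so 50/50, 30/70 and 20/80 are assumptions that show a range.

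**Reproducing the plan's figure.**
- Variance sum: 0.3 × 0.7 + 0.4 × 0.6 = 0.45.
- Children per arm before clustering: (1.960 + 1.282)² × 0.45 / 0.10² = 472.8.
- Design effect: 1 + (2 − 1) × 0.60 = 1.6.
- Caregivers per arm: 472.8 × 1.6 / 2 = 378.3, rounded up to 379, or 758 in total, as stated.
- Inflation: 758 / 0.85 = 891.8, so 892, or 446 per arm. The ITT population is everyone randomized, so 446 is used below.

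**Power within one level of a caregiver-level factor.** With n caregivers per arm in that level, SE = √(0.45 × 1.6 / (2n)) and power = Φ(0.10/SE − 1.96). The chance that exactly one of two levels is significant is P1(1 − P2) + P2(1 − P1). The true effect is 30% vs 40% in both levels.

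| Split | n per arm in each level | Power in each level | Exactly one significant |
|---|---|---|---|
| 50/50 | 223, 223 | 70%, 70% | 42% |
| 30/70 | 134, 312 | 49%, 84% | 51% |
| 20/80 | 89, 357 | 35%, 88% | 61% |

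For the 50/50 row: SE = √(0.45 × 1.6 / 446) = 0.0402, power = Φ(2.489 − 1.960) = 0.702, and 2 × 0.702 × 0.298 = 0.42. With 379 per arm the 50/50 and 20/80 figures become 47% and 63%.

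In all these settings a two-level interaction test at 0.05 would signal a difference about 5% of the time.

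**Age group.** Age belongs to the child, so siblings can fall in different strata. In the limiting case of two age strata with one child of every caregiver in each, a stratum holds 446 children per arm and no within-stratum clustering:
- SE = √(0.45 / 446) = 0.0318, and power = Φ(3.148 − 1.960) = 88%.
- Exactly one significant, tests treated as independent: 2 × 0.883 × 0.117 = 21%.
- Allowing a correlation of 0.6 between the two test statistics, both are significant with probability 0.814, so the figure is 2 × (0.883 − 0.814) = 14%.

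**Power of the interaction test.** For a caregiver-level factor, the SE of the difference between the two risk differences is √(SE1² + SE2²).
- 50/50: 0.0568. Power for a 10-point difference in effects is Φ(0.10/0.0568 − 1.96) = 42%, and the difference detectable with 80% power is (1.960 + 0.842) × 0.0568 = 16 points.
- 20/80: 0.0710, giving 29% and 20 points.

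These sums are on the risk-difference scale. SAP 6.2 reports an RR. With the same pair of rates in every level the effect is uniform on both scales.

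**The case against.** The best reply is that a reader might infer from SAP 6.5 that the team intends to contrast significant with non-significant subgroups and claim a differing effect. The documents do not say so. They say only that the analyses will be performed, on condition of adequate numbers. No objective in Protocol 4 or SAP 2 concerns effect modification, and the repeated model yields RRs with confidence intervals, not bare verdicts. This stands: the defect is a missing test and a missing rule of interpretation, not a planned invalid inference.

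A reader might also apply 42% to 61% to all three factors. That is not supported. The range assumes that a caregiver's children all sit in the same level, which can fail for age group, where the figure can be as low as 14% to 21%. The range also depends on assumed splits and on a true uniform 10-point effect.

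Nor can a family-wise false-positive rate be attached to the plan. It names three factors but no levels, and the same children appear under each factor, so neither the number of tests nor their independence is known.

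Finally, the interaction test is weak at this sample size. That is true and has to be disclosed. It is a reason for caution in reading the result, but does not justify relying on separate tests, which do not address the difference at all.

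**Conclusion.** The point holds. Both documents give within-subgroup repetition as the only method, and neither tests whether the app effect differs. For a two-level caregiver-level factor, under the plan's own design values with 446 caregivers per arm and a uniform effect, exactly one level would be significant in 42% (50/50) to 61% (20/80) of trials, against about 5% false signals from an interaction test. It does not follow that such contrasts will be claimed as effect modification, only that nothing in the plan prevents it.

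The primary result is not affected. The change is worth making before the analysis because it costs little and these subgroups matter to the trial's purpose.

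**What to change.** **SAP 6.5.**
- For each factor, fit the SAP 6.2 Poisson model in the full ITT population with the factor and its arm-by-subgroup terms added, keeping the site effect and the caregiver clustering. A single model also keeps siblings of different ages within their caregiver cluster.
- Report the interaction estimate on the RR scale with its 95% CI and p-value, and the subgroup RRs with 95% CIs from the same model.
- State that any claim of a differing effect rests on the interaction result and not on separate within-subgroup p-values.
- Label subgroup results exploratory. Three factors mean three interaction tests, and if these were independent the chance of at least one false signal would be 1 − 0.95³ = 14%.
- State that a non-significant interaction does not show equal effects.
- Fix the subgroup levels and the meaning of adequate numbers in advance, since both are now open.

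**Protocol 11.4.7.** Refer to the primary model without naming its form. Protocol 11.4.2 specifies a binomial model with a logit link while SAP 6.2 specifies Poisson, so naming Poisson in 11.4.7 would contradict 11.4.2.

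**Cost.** A few sentences and a few lines of code. No new data are needed, and the sample size and primary analysis do not change. The downside is the low power shown above, which the wording should disclose.

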6.6 SENSITIVITY ANALYSIS

While some participants may choose not to use the app beyond the initial download session, their outcomes will still be assessed and used to determine efficacy of the intervention. App interactions—or lack thereof—will be informative to understanding how participants engage with delivered content and how those interactions—or lack thereof—correlate with primary and secondary endpoints. The statistical team will use logistic regression analyses to determine the association between mHealth usage levels and completion or initiation of COVID-19 vaccine series.

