### 7.5.2 APP REGISTRATION AND USAGE (ADHERENCE)

During enrollment, site coordinators/research team members will ask participants if they would like assistance downloading and registering with the app. If participants request assistance, they will be scheduled with a Research Team member for technical assistance. After enrollment, caregiver participants will be block-randomized within their participating clinic by the enrolling site to either the Vaccine Uptake or General Health app study arms (see Section 8.2 for complete details on randomization). A Research Team member will then register the caregiver in the assigned app using their assigned study number as well as the caregiver participant's self-identified race, ethnicity, gender identity, rurality, and clinic of recruitment collected at enrollment. The Research Team will send caregiver participants the instructions on how to download their assigned app. Once downloaded, participants will enter their email address to retrieve their registration. The Research Team will follow up with participants who have not used the app within one week of registration/instructions successfully sent via telephone, email, or video conference to confirm the completion of app registration. Each time the app is opened, every selection made within the app will be tagged and recorded with both the caregiver participant's study number and a time date stamp. This data will be tracked throughout the caregiver participant's 24-week intervention to determine adherence (Section 8.3).

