#### **WEEK 8 ASSESSMENT**

**At the week 8 time point**, the caregiver participants will be sent a link to an assessment that asks for the following topics:

1. Vaccine status of eligible children

The surveys will ask caregiver participants for the dates, brands, and administrators for all COVID-19 vaccinations that any of their children received since enrollment, if any. For each vaccinated child, the survey will ask participants to upload a photo of the vaccination card. If a participant is unable to upload the photo or the writing on a card is illegible, the enrolling site personnel will contact the participant to schedule a time for a video conference to view and verify the card information.

2. Usability of the app

Surveys will include a systems usability assessment measured by the System Usability Scale (SUS). The SUS is a simple, ten-item scale giving a global view of subjective assessments of usability. SUS instructions will ask caregiver participants to record their immediate response to each item, rather than thinking about items for a long time. Responses range from Strongly Agree to Strongly Disagree. The SUS yields a single number representing a composite measure of the overall usability of the system. SUS scores have a range of 0 to 100, with 100 representing a perfect score.

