## 8.4 STUDY INTERVENTION COMPLIANCE

The study team will measure and monitor compliance using app usage analytics. The study team will summarize app usage measures as follows:

- Cumulative number of times app was accessed (sessions) to determine total content exposure
- Average session duration
- Median weekly app sessions to determine rate of engagement over time

**Title:** Improving pediatric COVID-19 vaccine uptake using an mHealth tool: a randomized, controlled trial

**PI:** [name]

- Number of unique content areas are accessed within the app
- Whether participants allowed receipt of push notifications

To be compliant to the intervention, participants must have at least one app session in which they access content from at least one app pathway.

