#### 11.4.8 SENSITIVITY ANALYSES

While some participants may choose not to use the app beyond the initial download session, their outcomes will still be assessed and used to determine efficacy of the intervention. App interactions—or lack thereof—will be informative to understanding how participants engage with delivered content and how those interactions—or lack thereof—correlate with primary and secondary endpoints. The statistical team will use logistic regression analyses to determine the association between mHealth usage levels and completion or initiation of COVID-19 vaccine series.

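### The app-usage regression neither defines usage nor requires it to precede vaccination, so use after the dose can create, mask or reverse the reported association

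*SAP*

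**What the plan says.** SAP 6.6 plans "logistic regression analyses to determine the association between mHealth usage levels and completion or initiation of COVID-19 vaccine series", and protocol 11.4.8 plans the same. The protocol gives the purpose: "App interactions—or lack thereof—will be informative to understanding how participants engage with delivered content", and how those interactions correlate with the endpoints. Neither section gives a usage measure, an exposure window, a lag, or a rule for handling the two arms.

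The candidate measures are in protocol 8.4. The first is "Cumulative number of times app was accessed (sessions) to determine total content exposure". The others are average session duration, median weekly sessions, number of content areas opened, and whether notifications were allowed. Protocol 7.5.2 gives the tracking period: "This data will be tracked throughout the caregiver participant's 24-week intervention to determine adherence".

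On the outcome side, SAP 6.2 counts completion as "whether or not the child initiates and completes the COVID-19 vaccine series during the 24 weeks of the intervention period". Initiation is counted over 16 weeks in SAP 6.3.1 and protocol 11.4.3, but to the end of week 24 in protocol 10.1.

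The timing data exist. Protocol 7.5.2 says that "every selection made within the app will be tagged and recorded with both the caregiver participant's study number and a time date stamp". On doses, the week 8 assessment in protocol 7.5.3 says: "The surveys will ask caregiver participants for the dates, brands, and administrators for all COVID-19 vaccinations".

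**The concern.** Exposure and outcome accrue over the same calendar period, and nothing puts one before the other. If use is totalled over 24 weeks and a child has a first dose in week 4, the remaining 24 − 4 = 20 weeks of use enter the initiation model as if they could have influenced that dose.

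Use may well change at vaccination, because the Vaccine Uptake app is built for deciding on and booking a vaccine. A caregiver who stops opening it afterwards looks like a low user whose child was vaccinated. One who opens it more afterwards looks like a high user whose child was vaccinated. The two patterns bias the result in opposite directions.

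This is the only planned model that relates amount of app use to vaccination. Readers will look to it to learn whether engagement matters, and its sign could reflect what caregivers did after the outcome.

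**Working it through.** **The plan's own figure.** The documents give no figure for the usage analysis. The sample size, used below only to set the number of caregivers, reproduces from 30% versus 40%, two-sided 0.05, power 0.90, intraclass correlation 0.60 and 2 children per caregiver (protocol 11.2, SAP 3.3):

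- Children per arm before clustering: (1.960 + 1.282)² × (0.30×0.70 + 0.40×0.60) / 0.10² = 10.507 × 0.45 / 0.01 = 472.8
- Caregivers per arm: 472.8 × (1 + 0.60) / 2 = 378.3, so 379, or 758 in total
- Inflation: 758 / 0.85 = 891.8, so 892

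**Windows.** If use is counted over 24 weeks and initiation over 16, then 24 − 16 = 8 weeks of use (weeks 17 to 24) fall after the outcome window for every child.

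**Simulation: assumptions, not document figures.** 892 caregivers with one outcome each; 30% complete; completion week uniform over weeks 4 to 24; sessions per week Poisson with a gamma-distributed caregiver rate (mean 1). The rate is multiplied either by a constant 0.5, or by a declining 1.0, 0.4 and 0.15 in weeks 1–8, 9–16 and 17–24, which mimics the front-loaded notifications. After the completing dose the rate is multiplied by *m*. Completion is independent of use before the dose, so the true odds ratio is 1. Completion is regressed on total use above versus below the median, with 300 runs per setting.

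**Expected direction.** Under constant use, a child who completes has on average 14 weeks before the dose (the mean of 4 to 24) and 10 after. Expected use relative to a child who does not complete is (14 + 10*m*) / 24. The ratio is 1 only when *m* = 1.

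| Use after dose (*m*) | (14 + 10*m*)/24 | OR, constant use (runs with p<0.05) | OR, declining use (runs with p<0.05) |
|---|---|---|---|
| 0 (stops) | 0.58 | 0.43 (100%) | 0.68 (78%) |
| 0.5 | 0.79 | 0.70 (67%) | 0.84 (19%) |
| 1 (unchanged) | 1.00 | 0.99 (6%) | 1.00 (5%) |
| 1.5 | 1.21 | 1.26 (37%) | 1.14 (15%) |
| 2 (doubles) | 1.42 | 1.53 (83%) | 1.28 (36%) |

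**With a true association.** An odds ratio of 1.5 was built in for above-median underlying use. Total use then gave the following (constant / declining):

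- use stops: 0.56 / 0.92
- use halves: 0.96 / 1.17
- use unchanged: 1.38 / 1.37
- use doubles: 2.15 / 1.80

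So a real association can be reversed, masked or inflated. The value below 1.5 when use is unchanged arises because observed counts measure the underlying rate imperfectly.

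**Two candidate repairs.**

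- *Cutting use at the dose.* With no true effect the odds ratio is 0.42–0.43 (constant) or 0.67–0.68 (declining), whatever happens later. Children who complete are then credited with 14 weeks of exposure on average against 24 for the rest, so this is biased too.
- *Week-8 landmark* (use in weeks 1–8, outcome after week 8 among those not yet complete). With no true effect the odds ratio is 0.98–1.01, and 2% to 8% of runs have p<0.05. The Monte Carlo standard error at 5% is √(0.05×0.95/300) = 1.3 points. With the built-in 1.5 it gives 1.32–1.38.

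**Cost of the landmark.** If dose timing is uniform, excluding children dosed by week 8 removes 8/24 = one third of vaccinated children, or 8/16 = one half of initiators under a 16-week window.

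**The case against.** The strongest reply has five parts.

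1. **The plan does not say that exposure is total 24-week use.** A reader might infer that it does. Protocol 8.4 lists five summaries, and 7.5.2 ties 24-week tracking to adherence, not to this regression. This stands: cumulative use is the natural reading, not the stated one. Leaving the choice open does not remove the problem, since nothing requires any of the measures to precede the dose.
2. **Use between doses is legitimate for completion.** A caregiver who returns to book a second dose does so before the series is complete. This also stands. The concern is use after the outcome being modelled, so it bites differently for initiation and completion.
3. **The sizes are assumed.** No document says how use changes after a dose, and with no change there is no bias of this kind. This stands; declining use also gives smaller distortions than constant use.
4. **Time ordering does not make the result causal.** Motivated caregivers may both use the app and vaccinate, and the simulation leaves this out by design. A landmark or time-updated model corrects order only.
5. **The stakes are limited.** The text claims association, and the randomised comparison answers whether the app works. This is right, and it sets the priority of the point.

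A reader might also infer that the arms are pooled, with General Health sessions counting the same as Vaccine Uptake sessions. The documents do not say so; they are silent. That is a gap to close, not a plan to criticise.

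**Conclusion.** The point holds as a matter of specification and time order. SAP 6.6 and protocol 11.4.8 leave the usage measure, its window and the handling of arms undefined, and allow use after the outcome to count as exposure. With no true effect and no confounding, the illustrative odds ratio runs from about 0.4–0.7 if use stops after the dose to about 1.3–1.5 if it doubles, and is about 1.0 if use is unchanged. The direction in this trial cannot be predicted from the documents.

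A reader might conclude that the trial's efficacy result is at risk. The documents do not support that: the primary intention-to-treat comparison does not use app sessions, and the sample size is unaffected. The conflict between 16 and 24 weeks for initiation is a separate inconsistency, which decides how much use falls after the outcome window. This is a cheap improvement to a supportive analysis.

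**What to change.** In SAP 6.6 and protocol 11.4.8:

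- **Name the usage measure** and its time unit before data lock, for example cumulative sessions by week.
- **Main usage model:** a discrete-time (pooled logistic) or time-to-event model of first dose, and one of completion, with a baseline term for week and cumulative use up to the previous week as a time-updated covariate. Allow for children clustered within caregiver, as SAP 6.2 does.
- **Completion model:** include doses already received as a time-updated term. Use between doses precedes completion, but it may be a reaction to the first dose, which itself brings the child closer to completion.
- **Arms:** fit within the Vaccine Uptake arm and show the General Health arm separately, as a guide to general engagement.
- **Optional check:** a week-8 landmark, stating the share of vaccinated children it excludes. Do not simply truncate use at the dose.
- **Window:** reconcile the 16- and 24-week definitions of initiation across SAP 6.3.1 and protocol 10.1 and 11.4.3.
- **Interpretation:** label the result associational, because motivation can still drive both use and vaccination.

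The cost is SAP wording and some extra programming. App selections are already time-stamped and dose dates are already collected, so no new data are needed.
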